### **6.3.6. Clinical Laboratory Assessments**

Refer to [Table 1](#) for clinical laboratory assessment time points.

The following laboratory assessments will be performed at a local laboratory:

Hematology: Complete blood count with differential

Comprehensive metabolite panel (Chemistry 14): ALT, albumin, alkaline phosphatase, aspartate aminotransferase (AST), direct and total bilirubin (and neonatal bilirubin for participants aged  $< 14$  days and neonates as defined in Cohort 2 presenting with jaundice), blood urea nitrogen, creatinine, eGFR using bedside Schwartz formula if  $\geq 1$  year of age, ionized calcium, carbon dioxide, chloride, total serum protein, potassium, sodium.

The smallest possible blood vials, such as microtainer tubes, should be used for participants weighing < 15 kg.

Clinical laboratory assessments at other days may be conducted if required by clinical need or local practice. The results of all clinical laboratory tests that are performed as part of clinical care, even if not required by the protocol, should be reported.

### **6.3.7. Age-Specific Assessments**

Refer to [Table 1](#) for the following age-specific assessments:

- Age:
  - Birth month and year for participants  $\geq 2$  years of age
  - Birth date for participant < 2 years of age
- Length and head circumference for participants < 2 years of age
- Best estimate of GA and PMA for participants with GA < 37 weeks and < 2 years of age
- Neonatal bilirubin panel for all participants < 14 days of age and any neonate as defined in Cohort 2 presenting with jaundice

### **6.3.8. Medically Attended Visits and Hospitalization**

Refer to [Table 1](#) for MAVs, hospitalization, intensive care unit (ICU), oxygen supplementation, and feeding support information collection time points.

Medically attended visit information includes any interactions with health care professionals other than study staff or designees including hospitalization; in-person emergency, urgent, or primary care visits; or any other in-person visit attended by the participant and a health care professional.

Hospitalization is defined as  $\geq 24$  hours of acute care in a hospital or similar acute care facility, including emergency rooms or temporary facilities instituted to address medical needs. This includes specialized acute medical care units within an assisted living facility or nursing home. This does not include hospitalization for the purposes of public health and/or clinical study execution.

If a participant is hospitalized, then the following will be collected, as applicable:

- oxygenation/oxygen supplementation information.
- feeding support information.

If a participant is admitted to the ICU during the study, then the ICU admission information will be collected, as applicable.

### **6.3.9. Pharmacokinetics**

[Table 2](#) summarizes the PK sample collection schedule. Blood samples will be collected relative to the study drug administered in clinic throughout the course of treatment. If 1 dose was administered in the evening of Day 1, PK samples can be collected on Day 6 relative to the study drug administered in clinic.

A full sampling scheme will be performed in at least the first 24 participants with  $\geq 6$  kg weight at baseline from Cohort 1 Part A. For the rest of participants in Cohort 1 Part A, as well as participants in Cohort 1 Part B and Cohort 2, reduced sampling schemes are considered as detailed in [Table 2](#).

A single PK sample should be collected on Day 5 ( $\pm 1$  day) for all participants who discontinue the study drug earlier than the last scheduled dose. A single PK sample should be collected at the early termination (ET) visit for all participants who discontinue study earlier than Day 10.

The PK sampling scheme ensures that the drawn blood volumes are within the daily and monthly recommended limits for the respective age/weight groups.

### **6.3.10. Clinical Virology**

#### **6.3.10.1. Virology Samples to Address Study Objectives**

Midturbinate nasal swab samples will be collected ([Table 1](#)) to assess RSV viral load by reverse transcriptase-quantitative polymerase chain reaction (RT-qPCR), respiratory coinfection by multiplex respiratory pathogen PCR, potential infectious viral titer assessment, and potential resistance testing (by sequencing and/or phenotyping). Nasal swabs will be collected by site personnel on days that the participant is present in the clinic or at participants home for sites with that service available.

#### **6.3.10.2. Virology Sample Storage**

Any remaining specimens from nasal swab samples collected during the study will be stored and retained for possible future virology-related testing. These stored samples may be used by the sponsor or its research partners for viral genotyping/phenotyping assays or their development, for retesting the amount of virus present in the sample, or for testing to learn more about how the study drug has worked or clinical laboratory testing to provide additional safety data. At the conclusion of this study, these samples may be retained in storage by Gilead for a period up to 15 years or per country requirements.

### 6.3.11. Questionnaires–Caregiver/Health Care Professional–Reported Outcomes

#### 6.3.11.1. Gilead RSV Caregiver Diary

CCI

. Previous qualitative and quantitative research established the content validity of the GRCD in populations of caregivers of children < 24 months of age who were hospitalized and not hospitalized due to RSV {[Lewis 2018](#)}. Additionally, a preliminary psychometric evaluation of the GRCD, conducted using data collected in the context of an observational primary data collection study in a usual care setting, supported the scoring and structure of the GRCD, as well as the validity, reliability, and responsiveness of the tool for assessing RSV in children < 24 months of age {[Williams 2018](#)}. CCI

CCI

CCI

CCI

CCI

The GRCD will be administered at all visits specified in [Table 1](#) and should be administered prior to study drug administration, where applicable. The GRCD should be ideally filled out by the same caregiver throughout the study.

CCI

#### 6.3.11.2. Global Impression of Severity Scales

CCI

The CGI-S and the HCPGI-S, with a 24-hour recall period, will be administered at all visits specified in [Table 1](#) and for days when ODV is administered, the questionnaire should be filled out prior to study drug administration.

CCI

#### 6.3.11.3. Global Impression of Change Scale

CCI

The CGI-C, with a recall period since they started the study drug, will be administered at all visits specified in [Table 1](#) and for days when ODV is administered, the questionnaire should be filled out prior to study drug administration.

CCI

#### 6.3.11.4. Health-related Quality of Life

The EuroQol-5 Dimensions (EQ-5D) is a health utility instrument that evaluates quality of life in 5 dimensions (mobility, self-care, usual activities, pain/discomfort, and anxiety/depression). The EQ-5D scale allows 243 unique health states or can be converted into EQ-5D index utility scores anchored at 0 for death and 1 for perfect health. The EQ-5D questionnaire also includes a visual analogue scale, by which respondents can report their perceived health status with a grade ranging from 0 (the worst possible health status) to 100 (the best possible health status) [{EuroQol Research Foundation 2024a}](#).

The EQ-5D-Y will be completed, by the caregiver for pediatric participants  $\geq 4$  years of age at screening (proxy reported), at all visits specified in [Table 1](#). The EQ-5D-Y assessment will not be required for participants  $< 4$  years of age at screening [{EuroQol Research Foundation 2024b}](#). The EQ-5D-5L will be completed by the caregiver at all visits specified in [Table 1](#).

For days when ODV is administered, both EQ-5D-Y (3 levels; EQ-5D-Y-3L) and EQ-5D-5L should be filled out prior to study drug administration.

#### 6.3.11.5. Work Productivity and Activity Impairment–Respiratory Syncytial Virus

The WPAI questionnaire is an instrument to measure impairments in work and activities. The scale consists of 6 questions that generate a scaled expression of 4 main outcomes: percentage of work missed due to health, percentage of impairment while working due to health, percentage of overall work impairment due to health, and percentage of activity impairment due to health.

The WPAI-RSV will be administered at all visits specified in [Table 1](#) and should be administered prior to study drug administration, where applicable.

The questionnaire is provided in Appendix [11.5.4](#).

#### 6.3.11.6. Palatability and Acceptability Questionnaires

To assess palatability and acceptability of study drug, the caregiver will rate acceptability and palatability of the applicable formulation using a 5-point facial recognition scale.

The caregiver may answer additional questions regarding preparation and dosing of the age-appropriate formulation.

The questionnaire will be administered at all visits specified in [Table 1](#) after study drug administration.

#### 6.3.11.7. Procedures to Minimize Missing Questionnaire Data

To minimize missing data, the following steps are put in place to help participants remain compliant with questionnaire completion per protocol-required time points:

- The caregiver may receive reminders/notifications on stipulated days ([Table 1](#)) to complete the questionnaire.
- Site staff and the study monitor will review questionnaire data completion reports to monitor compliance.
- Site staff will contact the caregiver regarding the missing data (or their close contact in case of nonresponse, where feasible).
- The caregiver may be provided with a Value Sheet (if available) to highlight the significance of questionnaire data and importance of participant compliance for the purpose of this study.

### 6.4. Procedures for Early Discontinuation From Study Intervention or From the Study

If a participant discontinues study intervention early (eg, as a result of an AE), every attempt should be made to keep the participant in the study and continue to perform study-related follow-up and procedures (Section [3.3](#)). If this is not possible or acceptable to the participant or investigator, the participant may be partially withdrawn from the study (Section [3.3.1.1.1](#)) to enable collection of study endpoint information or completely withdrawn from the study.

If a participant discontinues from the study early, the participant will be asked to return to the investigational site within 2 days to attend an ET visit for assessment and procedures specified in [Table 1](#).

#### 6.4.1. Loss to Follow-up

A participant will be considered lost to follow-up if the participant repeatedly fails to attend protocol-specified visits and is unable to be contacted by the study site.

The following actions must be taken if a participant fails to attend a scheduled protocol-specified visit (eg, in-person, telephone, or virtual):

- The site must attempt to contact the participant and reschedule the missed visit as soon as possible, counsel the participant on the importance of maintaining the protocol-specified at

least 3 attempts, including telephone calls, and if necessary, a certified letter to the participant's last known mailing address or local equivalent methods). These contact attempts should be documented in the participant's source documents.

- Should the participant continue to be unreachable and not responsive within 2 weeks, the participant will be considered lost to follow-up and will be withdrawn from the study, and no additional contact will be required.

#### **6.4.2. Procedures for End of Study**

A participant who completes or discontinues from the study early will have an end-of-study (or ET) visit for assessments and procedures specified in [Table 1](#).

#### **6.5. Sample Storage**

The stored biological samples may be used by Gilead or its research partner for additional testing to provide supplemental data to answer questions that relate to the main study. At the end of this study, these samples may be retained in storage by Gilead for a period up to 15 years or per country requirements, whichever is shorter.

## **7. ADVERSE EVENTS AND TOXICITY MANAGEMENT**

### **7.1. Definitions of Adverse Events and Serious Adverse Events**

#### **7.1.1. Adverse Events**

An AE is any untoward medical occurrence in a clinical study participant administered a study drug that does not necessarily have a causal relationship with the treatment. An AE can therefore be any unfavorable and/or unintended sign, symptom, or disease temporally associated with the use of a study drug, whether or not the AE is considered related to the study drug. Adverse events may also include pretreatment or posttreatment complications that occur as a result of protocol-specified procedures or special situations (Section 7.1.4).

- An AE does not include the following:
- Medical or surgical procedures such as surgery, endoscopy, tooth extraction, or transfusion. The condition that led to the procedure may be an AE and must be reported.
- Preexisting diseases, conditions, or laboratory abnormalities present or detected before the screening visit that do not worsen.
- Situations where an untoward medical occurrence has not occurred (eg, hospitalization for elective surgery, social and/or convenience admissions).
- Overdose without clinical sequelae (Section 7.1.4).
- Any medical condition or clinically significant laboratory abnormality with an onset date before the ICF is signed and not related to a protocol-associated procedure is not an AE but rather considered to be preexisting and should be documented as medical history.

Preexisting events that increase in severity or change in nature after study drug initiation or during or as a consequence of participation in the clinical study will also be considered AEs.

#### **7.1.2. Serious Adverse Events**

An SAE is defined as an event that, at any dose, results in the following:

- Death.
- A life-threatening situation (Note: the term “life-threatening” in the definition of “serious” refers to an event in which the participant was at risk of death at the time of the event; it does not refer to an event that hypothetically might have caused death if it were more severe.)
- Inpatient hospitalization or prolongation of existing hospitalization.

- Persistent or significant disability/incapacity.
- A congenital anomaly/birth defect.
- A medically important event or reaction: such events may not be immediately life-threatening or result in death or hospitalization but may jeopardize the participant or may require intervention to prevent 1 of the other outcomes constituting SAEs. Medical and scientific judgment must be exercised to determine whether such an event is reportable under expedited reporting rules. Examples of medically important events include intensive treatment in an emergency room or at home for allergic bronchospasm; blood dyscrasias or convulsions that do not result in hospitalization; and development of drug dependency or drug abuse.

### **7.1.3. Serious Adverse Drug Reaction**

A serious adverse drug reaction (SADR) is defined as any SAE that is considered causally related to the medicinal product at any dose administered.

### **7.1.4. Study Drugs and Gilead Concomitant Medications Special Situations Reports**

Special situations reports (SSRs) include all reports of medication error, abuse, misuse, overdose, occupational exposure, drug interactions, exposure via breastfeeding, unexpected benefit, transmission of infectious agents via the product, counterfeit of falsified medicine, and pregnancy regardless of an associated AE.

Medication error is any unintentional error in the prescribing, dispensing, preparation for administration or administration of a study drug while the medication is in the control of a health care professional, participant, or consumer. Medication errors may be classified as a medication error without an AE, which includes situations of missed dose, medication error with an AE, intercepted medication error, or potential medication error.

Abuse is defined as persistent or sporadic intentional excessive use of a study drug by a participant.

Misuse is defined as any intentional and inappropriate use of a study drug that is not in accordance with the protocol instructions or the local prescribing information.

An overdose is defined as an accidental or intentional administration of a quantity of a study drug given per administration or cumulatively that is above the maximum recommended dose as per protocol or in the product labeling (as it applies to the daily dose of the participant in question). In cases of a discrepancy in drug accountability, overdose will be established only when it is clear that the participant has taken the excess dose(s). Overdose cannot be established when the participant cannot account for the discrepancy, except in cases in which the investigator has reason to suspect that the participant has taken the additional dose(s).

Occupational exposure is defined as exposure to a study drug as a result of one's professional or nonprofessional occupation.

Drug interaction is defined as any report of drug/drug, drug/food, drug/alcohol, or drug/device interaction.

Unexpected benefit is defined as an unintended therapeutic effect where the results are judged to be desirable and beneficial.

Transmission of infectious agents is defined as any suspected transmission of an infected agent through a Gilead study drug.

Counterfeit or falsified medicine is defined as any study drug with a false representation of (a) its identity, (b) its source, or (c) its history.

## **7.2. Assessment of Adverse Events and Serious Adverse Events**

The investigator or qualified subinvestigator is responsible for assessing AEs and SAEs for causality and severity, and for final review and confirmation of accuracy of event information and assessments.

### **7.2.1. Assessment of Causality for Study Drugs and Procedures**

The investigator or qualified subinvestigator is responsible for assessing the relationship for each study drug using clinical judgment and the following considerations:

- **No:** evidence exists that the AE has an etiology other than the study drug. For SAEs, an alternative causality must be provided (eg, preexisting condition, underlying disease, intercurrent illness, concomitant medication).
- **Yes:** there is reasonable possibility that the AE may have been caused by the study drug.

A "reasonable possibility" of a causal relationship means that there is evidence, facts and/or other rationale to suggest a causal relationship, rather than a relationship that cannot be ruled out.

It should be emphasized that ineffective treatment should not be considered as causally related in the context of AE reporting.

The relationship to study procedures (eg, invasive procedures such as venipuncture or biopsy) should be assessed using the following considerations:

- **No:** evidence exists that the AE has an etiology other than the study procedure.
- **Yes:** the AE occurred as a result of protocol procedures (eg, venipuncture).

### **7.2.2. Assessment of Severity**

The severity of AEs will be graded using the Division of AIDS (DAIDS) Table for Grading the Severity of Adult and Pediatric Adverse Events, Toxicity Grading Scale, Version 2.1 {[Division of AIDS 2017](#)}. For each episode, the highest grade attained should be reported as defined in the Toxicity Grading Scale.

The DAIDS scale is available at:

<https://rsc.niaid.nih.gov/sites/default/files/daidsgradingcorrectedv21.pdf>

### **7.3. Investigator Reporting Requirements and Instructions**

#### **7.3.1. Requirements for Collection Before Study Drug Initiation**

After informed consent, but before initiation of study drug, all SAEs and any AEs that are related to protocol-required procedures must be reported on the applicable CRFs.

#### **7.3.2. Adverse Events**

Following initiation of study drug, collect all AEs, regardless of cause or relationship, until 30 days after last administration of study drug and report the AEs on the CRFs as instructed.

All AEs and clinically significant laboratory abnormalities should be followed until resolution or until the AE is stable, if possible. Gilead may request that certain AEs be followed beyond the protocol-defined follow-up period.

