## STUDY PROCEDURES TABLE

**Table 1. Study Procedures Table**

	Screening a,b	Baseline a					EOS	ET
Study Day		Day 1	Day 3 c	Day 5	Day 10	Day 21	Day 28	—
Visit Window	—	—	—	± 1 d	± 2 d	± 2 d	−4 d/+7 d	—
Type of Visit	In Person d					Virtual e		In Person d
Assent/caregiver consent	X							
Medical history f	X							
Demographics	X							
Documentation of RSV infection b	X							
Documentation of SARS-CoV-2 and influenza A/B test negativity b	X							
Inclusion/exclusion criteria	X	X						
Complete physical examination g	X				X			X
Symptom-directed physical examination g		X	X	X				
Body weight	X	X			X			X
Height/length/head circumference h	X				X			X
GA and PMA if GA is < 37 weeks for children < 2 years	X							
Vital signs i	X	X	X	X	X			X
Hematology, chemistry	X			X	X			X
Neonatal bilirubin panel for all participants < 14 days of age and any neonate as defined in Cohort 2 presenting with jaundice	X							
Nasal midturbinate swab samples j		X	X	X	X			X
GRCD k		By caregiver—from Days 1 through 28 or ET inclusive						

	Screening a,b	Baseline a					EOS	ET
Study Day		Day 1	Day 3 c	Day 5	Day 10	Day 21	Day 28	—
Visit Window	—	—	—	± 1 d	± 2 d	± 2 d	−4 d/+7 d	—
Type of Visit	In Person d					Virtual e		In Person d
CGI-S l		By caregiver—on Days 1, 3, 5, 10, 28 or ET						
CGI-C l		By caregiver—on Days 3, 5, 10, 28 or ET						
HCPGI-S m		X	X	X	X			X
WPAI-RSV n		By caregiver—on Days 1, 10, 28 or ET						
HRQOL questionnaires o		By caregiver—on Days 1, 5, 10, 28 or ET						
PK sample		Refer to Table 2						
Randomization		X						
Study drug dispensation		X						
Study drug administration p		Days 1 through 5 inclusive						
Study drug return q				X				
Concomitant medications	X	X	X	X	X	X	X	X
MAV/hospitalization/ICU information r	X	X	X	X	X	X	X	X
Oxygen supplementation requirements, if hospitalized	X	X	X	X	X	X	X	X
Feeding support information, if hospitalized	X	X	X	X	X	X	X	X
Adverse events	X	X	X	X	X	X	X	X
Acceptability and palatability assessment		X		X				

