- p Study drug will be administered twice daily, and administration times will be recorded by investigational site personnel or by the caregiver via a diary. Participants receiving only 1 of 2 doses on Day 1 will need to take their last dose on Day 6. Depending on site visit time, participants will be required to withhold their morning or evening dose prior to arriving to the site on Day 5 (or Day 3, if PK samples are collected on Day 3), as the dose will be administered at the site.
- q Study drug bottle should be returned by the participant on Day 5, if the participant has already completed both doses of study drug on that day. If the participant has study drug at the end of the Day 5 visit, the participant may return the study drug bottle during the subsequent in-person visit.
- r Medically attended visit information includes any interactions with health care professionals other than study staff or designees including hospitalization; in-person emergency, urgent, or primary care visits; ICU admission; or any other in-person visit attended by the participant and a health care professional.

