## 2. OBJECTIVES AND ENDPOINTS

Primary Objectives	Primary Endpoints

 
To evaluate the safety and tolerability of ODV in pediatric participants with RSV infection
 
	
 
Proportion of participants experiencing treatment-emergent adverse events (TEAEs) by Day 28
 
Proportion of participants experiencing Grade 3 or 4 treatment-emergent laboratory abnormalities (TELAs) by Day 28
 

 
To evaluate the efficacy of ODV on duration of time until alleviation of targeted RSV symptoms in pediatric participants with RSV infection
 
	
 
Time to alleviation of targeted RSV symptoms by Day 28
 

Secondary Objectives	Secondary Endpoints

 
To evaluate the plasma PK of ODV in pediatric participants with RSV infection
 
	
 
PK parameters (<math>AUC_{tau}</math>, <math>C_{max}</math>, and <math>C_{trough}</math>) for ODV metabolite, GS-441524
 

 
To evaluate the antiviral activity of ODV on RSV nasal swab viral load in pediatric participants with RSV infection
 
	
 
Change from baseline in RSV nasal swab viral load at Day 5
 

 
To evaluate the efficacy of ODV on duration of time until sustained alleviation of targeted RSV symptoms in pediatric participants with RSV infection
 
	
 
Time to sustained alleviation of targeted RSV symptoms by Day 28
 

 
To evaluate the efficacy of ODV on duration of time until resolution of targeted RSV symptoms in pediatric participants with RSV infection
 
	
 
Time to resolution of targeted RSV symptoms by Day 28
 

 
To evaluate acceptability and palatability of ODV in pediatric participants with RSV infection
 
	
 
Assessment of palatability and acceptability scores of the age-specific formulation as assessed by caregiver at Days 1 and 5
 

Exploratory Objectives	Exploratory Endpoints

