#### **7.3.3. Serious Adverse Events**

All SAEs, regardless of cause or relationship, that occur after the participant first consents to participate in the study (ie, signing the ICF) and throughout the duration of the study, including the posttreatment follow-up visit, must be reported on the applicable CRFs and to PS as instructed below in this section. This also includes any SAEs resulting from protocol-associated procedures performed after the ICF is signed. The investigator must report the primary cause of death for any participant who dies during the follow-up period to the sponsor.

Any SAEs and deaths that occur after the posttreatment follow-up visit but within 30 days of the last dose of study drug, regardless of causality, should also be reported.

Investigators are not obligated to actively seek SAEs after the protocol-defined follow-up period; however, if the investigator learns of any SAEs that occur after the protocol-defined follow-up period has concluded and the event is deemed relevant to the use of study drug, the investigator should promptly document and report the event to PS.

Instructions for reporting SAEs are described in Section [7.4.1](#).

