### **8.6.2. Adverse Events**

Clinical and laboratory AEs will be coded using the current version of the MedDRA. System organ class, high-level group term, high-level term, preferred term, and lowest-level term will be attached to the clinical database.

Events will be summarized based on the date of onset for the event. A TEAE will be defined as any AE that begins on or after the date of first dose of study drug up to the date of last dose of study drug plus 30 days.

Summaries (number and percentage of participants) of TEAEs (by system organ class and preferred term) will be provided by treatment group.

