7. SAFETY ANALYSES

Analysis of safety data will be conducted on the Safety Analysis Set, unless otherwise specified in the following sections. The treatment-emergent (TE) period is defined as the time period from the first dose date of study treatment up to and including 30 days after the last dose of study treatment.

All safety data during the TE period will be summarized by treatment group as defined in Section 3.2. Data for the pretreatment and treatment-free follow-up periods will be included in data listings.

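### The last scheduled AE contact may fall up to 4 days before the Day 28 primary safety endpoint, and on most permitted dates it falls short of the 30-day post-dose AE period

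*Protocol*

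**What the plan says.** **Endpoint.** Protocol Section 2 lists as a primary endpoint "Proportion of participants experiencing treatment-emergent adverse events (TEAEs) by Day 28". SAP 7.1.6 tabulates it separately from all treatment-emergent AEs.

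**Collection and analysis period.** Protocol 7.3.2 asks sites to "collect all AEs, regardless of cause or relationship, until 30 days after last administration of study drug". Protocol 8.6.2 counts an event as treatment-emergent if it starts on or after the first dose and "up to the date of last dose of study drug plus 30 days". SAP Section 7 takes the period from the "first dose date of study treatment up to and including 30 days after the last dose of study treatment". SAP 1.2 describes follow-up lasting at most 30 days from the final dose.

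**Last dose.** Table 1 places dosing on "Days 1 through 5 inclusive". Its footnote p adds: "Participants receiving only 1 of 2 doses on Day 1 will need to take their last dose on Day 6".

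**Last contact.** Protocol Table 1 and SAP Appendix 1 show AEs collected at each visit, ending with the virtual EOS visit at Day 28. Its window is −4/+7 days. No AE contact is scheduled after it.

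**After EOS.** Protocol 7.3.3 also requires reporting of SAEs and deaths that "occur after the posttreatment follow-up visit but within 30 days of the last dose of study drug". Neither document says how non-serious AEs arising after the EOS contact are to be obtained.

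**The concern.** Three clocks are in use: Day 28 for the primary endpoint, last dose plus 30 days for AE collection and the treatment-emergent period, and Day 24 to Day 35 for the final enquiry. A site can comply with the schedule and still make its last enquiry before either of the first two has run out.

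SAP 7.1.6 expresses the TEAE tables as numbers and percentages of the Safety Analysis Set, which is every dosed child. The SAP has rules for incomplete AE dates but none for incomplete AE follow-up. On a plain reading, a child last asked on Day 24 with nothing reported stays in the denominator as a non-event through Day 28. At stake is whether a primary safety proportion and the wider TEAE table rest on follow-up that the schedule secures.

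**Working it through.** No power or variance calculation is involved; the check is study-day arithmetic. SAP 3.8.1 sets the day of first dose as Day 1.

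**Inputs**
- EOS window (Table 1, SAP Appendix 1): 28 − 4 = Day 24 to 28 + 7 = Day 35.
- Last dose L (Table 1 and footnote p): Day 5, or Day 6 after a single dose on Day 1.
- End of AE period (Protocol 7.3.2 and 8.6.2, SAP 7): E = L + 30, so Day 35 or Day 36.

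**The plan's own figure.** The SAP 1.2 maximum of 30 days is reproduced for a Day 5 last dose with contact on the last permitted day: 35 − 5 = 30. For a Day 6 last dose the maximum is 35 − 6 = 29.

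**Primary endpoint.** Days without scheduled enquiry = 28 − contact day.
- Day 24: 4 days, or 4/28 = 14% of the period.
- Day 25: 3 days. Day 26: 2 days. Day 27: 1 day.
- Day 28 or later: none.

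**30-day post-dose period.** Days without scheduled enquiry = E − contact day, also shown as a share of 30.

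| EOS contact | Last dose Day 5 (E = 35) | Last dose Day 6 (E = 36) |
|---|---|---|
| Day 24 | 11 (37%) | 12 (40%) |
| Day 28 | 7 (23%) | 8 (27%) |
| Day 35 | 0 | 1 (3%) |

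So only a Day 35 contact closes the period for a Day 5 finisher. No in-window contact closes it for a Day 6 finisher, although the best case misses by a single day.

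**The remedies**
- A 0/+7 window (Day 28 to Day 35) brings the primary endpoint gap to 0. The 30-day gap is still 0 to 7 days (Day 5 finisher) or 1 to 8 days (Day 6 finisher).
- A contact at L + 30 or just after brings both gaps to 0. Even for a child who stops after Day 1, L + 30 = Day 31, which is past Day 28.

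**The case against.** The strongest reply is that the reporting duty does not stop at EOS. Protocol 7.3.2 ties collection to the last dose and not to a visit, so an event volunteered by a caregiver or found at an unscheduled contact still counts. Protocol 7.3.3 covers late SAEs and deaths. This stands. A reader might infer that the 30-day period can never be covered after a Day 6 last dose, or that the endpoint itself ends early. The documents do not support either inference. What is missing is a scheduled prompt for non-serious events.

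Second, the child is not out of sight after a Day 24 call. The caregiver diary runs through Day 28, several questionnaires fall on Day 28, and Protocol 3.4.2 treats a child as finished only when all study periods are complete. This stands against any claim that nobody asks anything on Days 25 to 28. It does not close the gap, because Table 1 describes the diary as a symptom assessment and not as AE collection.

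Third, the days at issue for the primary endpoint are late. The first is Day 25, which is 25 − 6 = 19 or more days after the last dose. The window is the same in both arms of a blinded trial, and the safety analysis is descriptive. All of this stands, and it limits the likely effect.

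Fourth, the study was terminated early (SAP 1 and 2.2), so a new window cannot alter these data. The SAP 4.1 disposition listing already gives dose dates and end-of-study dates by child. This is largely right, but a listing is not a per-arm count beside the TEAE tables, and the SAP does not say that the listed end-of-study date is the AE contact date.

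**Conclusion.** The point holds as a mismatch between the contact schedule and two safety periods. For the primary endpoint, scheduled enquiry can end 1 to 4 days early, and only when the EOS contact falls on Days 24 to 27. For the 30-day period the shortfall arises in ordinary conduct: 7 or 8 days after a contact on nominal Day 28, and 11 or 12 days at worst. The 23% and 37% figures belong to the wider TEAE table and should not be read as loss on the primary endpoint.

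The consequence is possible under-ascertainment of non-serious AEs in both arms. A reader might infer a biased treatment comparison; nothing in the documents shows that contact timing differs between arms. Shares of days are not shares of events. The documents do not give the number of early EOS contacts, of Day 6 finishers or of late AEs, so missed events cannot be computed. The conclusion assumes that sites use the full permitted window and make no AE enquiry beyond Table 1. The matter should be corrected, with a small to moderate expected effect.

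**What to change.** **For the final analysis of this study.** Beside the TEAE tables, report per arm the number of children whose last AE contact was (a) before Day 28 and (b) before last dose plus 30 days, showing those who left the study early separately. Use the EOS contact date. The Last Study Date in SAP 3.8.1 takes in questionnaire dates, so a Day 28 questionnaire entry could conceal a Day 24 AE contact. The cost is one small table from data already collected.

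**For any amendment or reuse of the protocol.** In Protocol Table 1 and SAP Appendix 1, change the EOS window from −4/+7 to 0/+7 days, so that scheduled enquiry always reaches Day 28. That alone does not cover the 30-day period. To cover both, time the same virtual contact at or just after last dose plus 30 days, and reconcile Table 1, Protocol 7.3.2 and 8.6.2, SAP 1.2 and SAP 7 so that they describe one period. No visit is added. The cost is amendment wording and the loss of early flexibility for sites; the later timing also moves the last contact to Day 35 or Day 36 for children who complete dosing.
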